## 6.5 POOLING OF CENTRES

This section is not applicable, because the study was performed in only one centre.

## 6.6 HANDLING OF MISSING DATA AND OUTLIERS

Handling of missing data and outliers will be performed as described in the CTP, Section 7.3.

The only exceptions where imputation might be necessary for safety evaluation are AE dates. Missing or incomplete AE dates are imputed according to BI standards (see “Handling of Missing and Incomplete AE Dates”) (3).

Missing data and outliers of PK data are handled according to BI standards (see “Standards and processes for analyses performed within Clinical Pharmacokinetics/Pharmacodynamics” (4) and “Noncompartmental Pharmacokinetic / Pharmacodynamic Analyses of Clinical Studies” (5)).

## 6.7 BASELINE, TIME WINDOWS AND CALCULATED VISITS

For each treatment period, the baseline value is defined as the last available off-treatment measurement before administration of BI 1358894 of the respective treatment period.

**Section 6.1 of the CTP:** *Study measurements and assessments scheduled to occur ‘before’ trial medication administration on Day 1 are to be performed and completed within a 3 h-period prior to the trial drug administration.*

*Up to 48 h after drug administration (planned time), the acceptable deviation from the scheduled time for adverse event/concomitant medication questioning, suicidality assessment,*

*vital signs, ECG, and laboratory tests will be  $\pm$  30 min, if not stated otherwise in the CTP Flow Chart,*

*Starting from planned time of 48 hours until 168 hours (not inclusive) after drug administration (and beyond) a time window of  $\pm$  120 minutes will be allowed for all procedures*

*Starting from a planned time of 168 hours after drug administration (and beyond) a time window of  $\pm$  26 hours will be allowed for all procedures*

In addition the following time windows will be considered acceptable for PK sampling up to 48 hours after each study drug administration:

Starting from planned time of 0 hours until 2 hours (not inclusive) after drug administration a time window of  $\pm$  5 minutes will be allowed. Starting from planned time of 2 hours until 48 hours (not inclusive) after drug administration a time window of  $\pm$  10 minutes will be allowed.

Adherence to time windows will be checked via the consistency check listings at the RPM.

Unscheduled measurements of laboratory data, vital signs data, for adverse event/concomitant medication questioning, suicidality assessment and ECG data will be assumed to be repeat measurements of the most recent scheduled measurement (e.g. for follow-up or confirmation of a particular value). Therefore, unscheduled measurements will be assigned to the planned time point of the previous scheduled measurement.

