5.2.3 Safety laboratory parameters

For the assessment of laboratory parameters, blood and urine samples will be collected by the trial site at the times indicated in the Flow Chart after the subjects have fasted for at least 9 h. For retests, at the discretion of the investigator or designee, overnight fasting is not required.

The parameters to be assessed are listed in Tables [5.2.3: 1](#) and [5.2.3: 2](#). Reference ranges will be provided in the ISF.

Manual differential white blood cell count or urine sediment examinations will only be performed if there is an abnormality in the automatic blood cell count or in the urinalysis, respectively.

[REDACTED]

Proprietary confidential information © 2022 Boehringer Ingelheim International GmbH or one or more of its affiliated companies

Table 5.2.3: 1

Routine laboratory tests

Functional lab group	BI test name [comment/abbreviation]	A	B	C
Haematology	Haematocrit Haemoglobin Red Blood Cell Count/Erythrocytes White Blood Cells/Leucocytes Platelet Count/Thrombocytes (quant) Erythrocyte Sedimentation Rate 1 h	X X X X X X	X X X X X X	X X X X X X
Automatic WBC differential, relative	Neutrophils/Leukocytes; Eosinophils/Leukocytes; Basophils/Leukocytes; Monocytes/Leukocytes; Lymphocytes/Leukocytes	X	X	X
Manual differential WBC (if automatic differential WBC is abnormal)	Neut. Poly (segs)/Leukocytes; Neutrophils Bands/Leukocytes; Eosinophils/Leukocytes; Basophils/ Leukocytes; Monocytes/Leukocytes; Lymphocytes/Leukocytes			
Coagulation	Activated Partial Thromboplastin Time Prothrombin time Prothrombin time – INR (International Normalization Ratio)	X X X	-- -- --	-- -- --
Enzymes	AST [Aspartate aminotransferase] /GOT, SGOT ALT [Alanine aminotransferase] /GPT, SGPT Alkaline Phosphatase Gamma-Glutamyl Transferase Creatine Kinase [CK] Creatine Kinase Isoenzyme MB [only if CK is elevated]	X X X X X X	X X X X -- --	X X X X -- --
Hormones	Thyroid Stimulating Hormone	X	--	--

Substrates	Glucose (Plasma) Creatinine GFR/ CKD-EPI Bilirubin, Total Bilirubin, Direct Protein, Total C-Reactive Protein (Quant)	X X X X X X	X X X X X X	X X X X X X
------------	---	----------------------------	----------------------------	----------------------------

* In male subjects only

Table 5.2.3: 1

Routine laboratory tests (cont.)

Functional lab group	BI test name [comment/abbreviation]	A	B	C
Electrolytes	Sodium Potassium	X X	X X	X X

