5.2.6.1.4 Adverse events of special interest

The term adverse events of special interest (AESI) relates to any specific AE that has been identified at the project level as being of particular concern for prospective safety monitoring and safety assessment within this trial, e.g. the potential for AEs based on knowledge from other compounds in the same class. AESIs need to be reported to the sponsor's Pharmacovigilance Department within the same timeframe that applies to SAEs, please see Section [5.2.6.2.2](#).

The following are considered as AESIs:

- Potential severe DILI

A potential severe Drug Induced Liver Injury (DILI) that requires follow-up is defined by the following alterations of hepatic laboratory parameters:

- o An elevation of AST (aspartate aminotransferase) and/or ALT (alanine aminotransferase) ≥ 3 -fold ULN combined with an elevation of total bilirubin ≥ 2 -fold ULN measured in the same blood sample, or in samples drawn within 30 days of each other, or
- o Aminotransferase (ALT, and/or AST) elevations ≥ 10 -fold ULN

These lab findings constitute a hepatic injury alert and the subjects showing these lab abnormalities need to be followed up according to the 'DILI checklist' provided via eDC. In case of clinical symptoms of hepatic injury (icterus, unexplained encephalopathy, unexplained coagulopathy, right upper quadrant abdominal pain, etc.) without lab results (ALT, AST, total bilirubin) available, the Investigator should make sure that these parameters are analysed, if necessary in an unscheduled blood test. Should the results meet the criteria of hepatic injury alert, the procedures described in the DILI checklist should be followed.

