7.2.5 Safety analyses

Safety will be analysed based on the assessments described in Section [2.2.2.2](#). All treated subjects (TS, refer to Section [7.2](#)) will be included in the safety analysis. Safety analyses will be descriptive in nature and based on BI standards. No hypothesis testing is planned.

For all analyses, the treatment actually administered (= treatment at onset) to the subject will be used (any deviations from the randomised treatment will be discussed in the minutes of the Report Planning Meeting).

Treatments will be compared in a descriptive way. Tabulations of frequencies/proportions will be used to evaluate categorical (qualitative) data, and tabulations of descriptive statistics will be used to analyse continuous (quantitative) data.

Measurements (such as ECG, vital signs, or laboratory parameters) or AEs will be assigned to treatments (see Section [4.1](#)) based on the actual treatment at the time of the measurement or on the recorded time of AE onset (concept of treatment emergent AEs). Therefore, measurements performed or AEs recorded prior to first intake of trial medication will be assigned to the screening period, those between first trial medication intake and end of REP (see Section [1.2.2](#)) will be assigned to the respective treatment period. Events occurring after the REP but prior to next intake or end of trial termination date will be assigned to 'follow-up'. In case of two or more treatments, the follow-up will be summarized according to the previous treatment. These assignments including the corresponding time intervals will be defined in detail in the TSAP. Note that AEs occurring after the last per protocol contact but entered before final database lock will be reported to Pharmacovigilance only and will not be captured in the trial database.

Additionally, further treatment intervals (analysing treatments) may be defined in the TSAP in order to provide summary statistics for time intervals, such as combined treatments, on-treatment totals, or periods without treatment effects (such as screening and follow-up intervals).

Adverse events will be coded using the Medical Dictionary for Regulatory Activities (MedDRA). Frequency, severity, and causal relationship of AEs will be tabulated by treatment, system organ class, and preferred term. SAEs, AESIs (see Section [5.2.6.1](#)), and other significant AEs (according to ICH E3) will be listed separately.

Relevant ECG findings will be reported as AEs.

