**C) Appendix 16.2 of CTR: all AEs will be listed.**

Measurements will be considered on-treatment, if they were taken within the on-treatment phases as defined in [Table 6.1: 2](#).

For detailed information on the handling of the treatments refer to Technical TSAP ADS plan and Analysis Data Reviewers guide.

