## **7.8.2      Laboratory data**

The analyses of laboratory data will be descriptive in nature and will be based on BI standards “Handling, Display and Analysis of Laboratory Data” ([12](#)).

Analyses will be based on normalised values, which means transforming to a standard unit and a standard reference range. The original values will be analysed if the transformation into standard unit is not possible for a parameter.

Laboratory data will be analysed qualitatively via comparison of laboratory data to their reference ranges. Values outside the reference range as well as values defined as possibly clinically significant will be flagged in the data listings.

Clinically relevant findings in laboratory data will be reported as baseline conditions (at screening) or as AEs (during the trial) if judged clinically relevant by the investigator, and will be analysed as such. It is the investigator's responsibility to decide whether a lab value is clinically significantly abnormal or not (at the RPM at the latest).

Descriptive statistics of laboratory data over time including change from baseline (see [Section 6.7](#)) will be calculated by planned time point based on the worst value of the subject at that planned time point (or assigned to that planned time point).

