## **7.8.3      Vital signs**

The analyses of vital signs (blood pressure and pulse rate) will be descriptive in nature. Descriptive statistics of vital signs over time and for the difference from baseline (see [Section 6.7](#)) will be provided.

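### Unless overridden elsewhere, SAP 6.7 labels an unscheduled laboratory draw made between dosing and the 24:00 sample as pre-dose

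*SAP*

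**What the plan says.** - **Assignment rule.** SAP 6.7 presumes that an unscheduled laboratory, vital-sign or ECG value repeats the latest scheduled one. It concludes that "unscheduled measurements will be assigned to the planned time point of the previous scheduled measurement". Dosing is not mentioned.
- **Laboratory tables.** SAP 7.8.2 gives descriptive statistics by planned time, including change from baseline, "based on the worst value of the subject at that planned time point (or assigned to that planned time point".
- **Vital-sign tables.** SAP 7.8.3 plans "Descriptive statistics of vital signs over time and for the difference from baseline" and states no worst-value rule.
- **Analysis phase.** Protocol 7.2.5 assigns measurements and adverse events to treatments "based on the actual treatment at the time of the measurement or on the recorded time of AE onset". SAP 6.1 agrees: "Measurements will be considered on-treatment, if they were taken within the on-treatment phases" of Table 6.1: 2.
- **Baseline.** In SAP 6.7, for each period, "the baseline value is defined as the last available off-treatment measurement before administration of BI 1358894".
- **Why unscheduled values arise.** Protocol 5.2.3 provides for repeats: "For retests, at the discretion of the investigator or designee, overnight fasting is not required". Protocol 5.2.6.1.4 provides for a different case. If there are clinical symptoms of liver injury and no results are available, the investigator is to ensure that "these parameters are analysed, if necessary in an unscheduled blood test".

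**The concern.** The rule suits a true retest: a doubtful -1:00 result that is repeated belongs with -1:00. It does not suit a draw prompted by something new after the tablet was taken, which is not a repeat of the pre-dose sample. Because the rule does not stop at drug administration, such a draw is filed under a time before the dose.

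At stake is how the by-time-point safety tables read. A laboratory value obtained under a treatment could be shown as that treatment's pre-dose value, and the scheduled post-dose rows would show nothing of it. The plan would also give one draw a pre-dose planned time and an on-treatment phase without saying which of the two decides its row.

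**Working it through.** The plan gives no figure to reproduce. The check applies the rule to the schedule.

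**Inputs**
- Safety laboratory in each period (Flow Chart): -1:00, 24:00, 240:00. Protocol 5.2.3 assigns this laboratory set to Visits 2 to 5, so to all four periods. The Day -1 admission tests are only drug, alcohol and pregnancy tests (Flow Chart, footnote 5).
- Vital signs in each period (Flow Chart): -1:00, 4:00, 8:00, 24:00, 34:00.
- The -1:00 procedures must be finished before dosing (Flow Chart, footnote 2).
- Subjects: 24 planned, including up to 4 drop-outs (Protocol 7.5), so 20 to 24 per row.

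**Step 1: the label.** Assigned time = the largest planned time not later than the actual time.

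| Measurement | Actual time after dosing | Assigned time |
|---|---|---|
| Laboratory | 6 h | -1:00 |
| Laboratory | 23.5 h | -1:00 |
| Laboratory | 24.5 h | 24:00 |
| Laboratory | 100 h | 24:00 |
| Vital signs | 2 h | -1:00 |
| Vital signs | 3.5 h | -1:00 |
| Vital signs | 4.5 h | 4:00 |
| Vital signs | 10 h | 8:00 |

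On a 15-minute grid, every laboratory time from 0.25 to 23.75 h and every vital-sign time from 0.25 to 3.75 h falls on -1:00. In practice each window ends at the actual time of the scheduled 24 h draw or 4 h reading, which may vary by 30 minutes.

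**Step 2: other attributes of a 6 h laboratory draw**
- Planned time (SAP 6.7): -1:00.
- Phase (SAP 6.1, Protocol 7.2.5): on-treatment.
- Baseline (SAP 6.7): not eligible, because it was taken after dosing.

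The phase and baseline rules are sound, but neither changes the planned time.

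**Step 3: the laboratory table.** The -1:00 row now has two candidates for this subject. If the 6 h value is the worse, SAP 7.8.2 selects it and the true pre-dose value is displaced. If it is not, the true value stands. In both cases the 6 h draw enters no post-dose row.

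**Step 4: size.** If the 6 h value differs from the true pre-dose value by d and is selected, the row mean moves by d/n:
- n = 24: d/24 = 0.042d
- n = 20: d/20 = 0.050d

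Illustration with assumed values that are not in the documents: all 24 pre-dose ALT values are 25 and one 6 h value is 90, so d = 65. The -1:00 mean becomes (23 × 25 + 90)/24 = 665/24 = 27.7 instead of 25.0, a shift of 65/24 = 2.7. The row maximum becomes 90 instead of 25. That subject's baseline remains 25.

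**Step 5: vital signs.** Step 1 gives the same wrong label, but with no worst-value rule in SAP 7.8.3 the text does not say whether an unscheduled value would enter the table. Only the label can be shown.

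**The case against.** The strongest objection is that the relevant rule may exist out of sight. By its title, Table 6.1: 2 covers the actual treatment used for laboratory, vital-sign and ECG data, and its body is not in the public text. SAP 6.1 refers details of treatment handling to a technical plan, and SAP 7.8.2 rests on an internal laboratory standard. The table layout is not shown either: a table split by phase, or one whose pre-dose row displays the defined baseline, would keep the post-dose value out. This stands, and makes the point conditional.

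It can also be said that planned time and analysis phase are separate attributes, so different values are no contradiction. That is right: a reader might infer that SAP 6.7 contradicts Protocol 7.2.5, but the text supports only an unresolved tension.

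The trigger is narrow too. A draw must be made within 24 h of a single dose, for a new reason, and be that subject's worst value at that planned time. A clinically relevant result would still be reported as an adverse event, listed individually and flagged if out of range. This limits the consequence. It does not repair the rule, which is stated without exception and rests on a premise that Protocol 5.2.6.1.4 shows need not hold.

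**Conclusion.** The point holds in a limited, conditional form and is minor. As written, SAP 6.7 gives a pre-dose planned time to any unscheduled laboratory draw between dosing and the 24:00 sample, and SAP 7.8.2 can carry that value into the pre-dose row. The mean shift is d/24 to d/20 per selected value. The documents give no rate of unscheduled draws, so the number of affected values is unknown and may be zero.

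This assumes that neither Table 6.1: 2 nor the laboratory standard overrides the rule, that the table has a -1:00 row filled by planned time, and that the residual effect period, whose length is not in the public text, covers the first 24 h.

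Three stronger readings are not supported:
- **Baseline is contaminated.** It is not: baseline must precede administration, so the reference for change from baseline is protected.
- **A safety signal would be lost.** Individual listings, out-of-range flags, adverse events and events of special interest do not depend on the planned-time label. Pharmacokinetic results are untouched.
- **The long window means much affected data.** The 24 h after each dose is elapsed time in which a draw could fall, not a count of misplaced values.

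For vital signs between dosing and 4:00 the label is wrong, but no effect on a table is established.

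**What to change.** Add to SAP 6.7 that an unscheduled measurement is never assigned to a planned time on the other side of a drug administration. One taken after dosing and before the first scheduled post-dose time is treated as post-dose and on-treatment. It is kept out of the pre-dose row and shown at its actual time, at least in the listing. A separate post-dose unscheduled row with its N is optional; it would usually hold very few, selected subjects and should not be compared with the scheduled rows.

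Retests before dosing, and unscheduled values after the first scheduled post-dose time, keep their present assignment. The worst-value rule in SAP 7.8.2 needs no change. If Table 6.1: 2 or the laboratory standard already prevents the problem, a cross-reference in SAP 6.7 is enough.

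The cost is one sentence, one date-time condition in the derivation, and a small departure from the company convention.

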## 7. PLANNED ANALYSIS

Safety analysis (refer to [Section 7.8](#)) will be performed by the [REDACTED] and will be presented in Sections 15.1 to 15.4 of the CTR and in Appendix 16.2 and 16.1.13.1.

Inferential statistical analyses of PK endpoints (refer to [Section 7.4](#) and [Section 7.5.2](#)) will also be performed by the [REDACTED] and will be presented in Section 15.5 of the CTR and in Appendix 16.1.13.3.

Descriptive data analysis of PK endpoints and concentrations will be performed by the [REDACTED] and will be presented in Section 15.6 of the CTR and in Appendix 16.1.13.3.

The format of the listings and tables will follow the BI standards (see “Standards for Reporting of Clinical Trials and Project Summaries” ([6](#)) with the exception of those generated for PK-calculations following BI standards for PK/PD analysis ([7](#)).

The individual values of all subjects will be listed, sorted by treatment sequence, subject number and visit, except for listings regarding PK, which will be sorted by treatment, subject number and planned time. The listings will be included in Appendix 16.2 and for PK in Appendix 16.1.13 of the CTR.

For end-of-text tables, the set of summary statistics for non-PK parameters is:

N	number non-missing observations
Mean	arithmetic mean
SD	standard deviation
Min	minimum
Median	median
Max	maximum

For analyte concentrations, the following descriptive statistics will additionally be calculated:

CV	arithmetic coefficient of variation
gMean	geometric mean
gCV	geometric coefficient of variation

For PK parameters, the following descriptive statistics will additionally be calculated:

P10	10 th percentile
Q1	1 st quartile
Q3	3 rd quartile
P90	90 th percentile

The descriptive statistics of concentrations will be displayed with three significant digits. The descriptive statistics of PK parameters will be calculated using the individual values with the number of decimal places as provided by the evaluation program. Then the individual values as well as the descriptive statistics will be reported with three significant digits in the CTR.

Tabulations of frequencies for categorical data will include all possible categories and will display the number of observations in a category as well as the percentage (%) relative to the respective treatment group (unless otherwise specified, all subjects in the respective subject set whether they have non-missing values or not).

Percentages will be given in integer numbers due to the small sample size of <100. The category missing will be displayed only if there are actually missing values.

#### Main comparisons of interest

The main comparisons of interest in this trial to assess relative bioavailability are the following:

- i)  $T_{\text{fasted}}$  versus  $R_{\text{fasted}}$
- ii)  $T_{\text{fed}}$  versus  $R_{\text{fed}}$
- iii)  $T_{\text{fed}}$  versus  $T_{\text{fasted}}$
- iv)  $R_{\text{fed}}$  versus  $R_{\text{fasted}}$

In the remaining document treatment A represents the first, and treatment B the second treatment of each pairwise comparison stated above.

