Test product	BI 1358894, iCF (T), film-coated tablets, dose strength 100 mg
dose	100 mg (1 x 100 mg)
mode of administration	Oral administration in fasted (overnight fast of at least 10 hours) and fed state (treatments T _{fasted} and T _{fed}) with 240 mL of water

Proprietary confidential information © 2022 Boehringer Ingelheim International GmbH or one or more of its affiliated companies

Reference product	BI 1358894, TFII (R), film-coated tablets, dose strength 50 mg
dose	100 mg (2 x 50 mg)
mode of admin.	Oral administration in fasted (overnight fast of at least 10 hours) and fed state (treatments R_{fasted} and R_{fed}) with 240 mL of water
Duration of treatment	One day (single dose) for each treatment
Statistical methods	
Relative bioavailability will be estimated by the ratios of the geometric means of the respective pairwise comparison of interest for the primary and secondary endpoints, i.e. for the two tablet formulations under fasted or fed condition and the food effect for each formulation. Additionally, their two-sided 90% confidence intervals (CIs) will be provided. This method corresponds to the two one-sided t-test procedure, each at a 5% significance level. Since the main focus is on estimation and not testing, a formal hypothesis test and associated acceptance range is not specified for any comparison of interest. The statistical model will be an analysis of variance (ANOVA) on the logarithmic scale including effects for sequence, subjects nested within sequences, period and treatment. CIs will be calculated based on the residual error from the ANOVA.
 
Descriptive statistics will be calculated for all endpoints.

FLOW CHART

Period	Visit	Day	Planned time (relative to drug administration) [h:min]	Approximate clock time of actual day [h:min]	Event and comment	Safety laboratory ⁹	PK blood	12-lead ECG	Suicidality Assessment ⁸	Vital signs (BP, PR)	Counselling on contraceptive measures ¹⁰	Questioning for AEs and concomitant therapy ⁶
SCR	1	-21 to -2			Screening (SCR) ¹	X ^A		X	X	X	X	
1/2/3/4 (four periods separated by a wash-out period of at least 17 days) 2/3/4/5	2/3/4/5	-1	-12:00	20:00	Admission to trial site	X ⁵			X		X	X
			-1:00	07:00	Allocation to treatment ² (visit 2 only)	X ^{2,B}	X ²	X ²		X ²		X ²
			-0:30	07:30	High fat, high calorie breakfast ⁷							
			0:00	08:00	Drug administration							
			0:30	08:30			X					
			1:00	09:00			X					
			1:30	09:30			X					
			2:00	10:00	240 mL fluid intake		X					
			3:00	11:00			X					

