2. TRIAL OBJECTIVES AND ENDPOINTS

2.1 MAIN OBJECTIVES, PRIMARY AND SECONDARY ENDPOINTS

2.1.1 Main objectives

To investigate the relative bioavailability of the intended Commercial Formulation (iCF) (Test, T) compared with Trial Formulation 2 (TFII) (Reference, R) and to assess potential food effects following oral administration of BI 1358894.

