7. STATISTICAL METHODS AND DETERMINATION OF SAMPLE SIZE

7.1 NULL AND ALTERNATIVE HYPOTHESES

The relative bioavailability of the interested treatment comparisons:

- i) T_{fasted} versus R_{fasted}
- ii) T_{fed} versus R_{fed}
- iii) T_{fed} versus T_{fasted}
- iv) R_{fed} versus R_{fasted}

will be estimated by the ratios of the geometric means (treatment A/treatment B, with A, B representing first, respectively second treatment of each pairwise comparisons stated above), and their corresponding 2-sided 90% confidence intervals (CIs) will be provided. This method corresponds to the two one-sided t-test procedure, each at the 5% significance level. Since the main focus is on estimation and not testing, a formal hypothesis test and associated acceptance range is not specified.

Due to the exploratory nature of the assessment, no significance level adjustment for investigating multiple comparisons will be applied.

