7.2.2 Primary endpoint analyses

Primary analyses

The statistical model used for the analysis of the primary endpoints will be an analysis of variance (ANOVA) model on the logarithmic scale. That is, the PK endpoints will be log-transformed (natural logarithm) prior to fitting the ANOVA model. This model will include effects accounting for the following sources of variation: sequence, subjects within sequences, period and treatment.

Proprietary confidential information © 2022 Boehringer Ingelheim International GmbH or one or more of its affiliated companies

The effect 'subjects within sequences' will be considered as random, whereas the other effects will be considered as fixed. The model is described by the following equation:

$$y_{ijkm} = \mu + \zeta_i + s_{im} + \pi_j + \tau_k + e_{ijkm}, \text{ where}$$

y_{ijkm} = logarithm of response measured on subject m in sequence i receiving treatment k in period j,

μ = the overall mean,

ζ_i = the i^{th} sequence effect, $i = 1, 2, 3, 4$

s_{im} = the effect associated with the m^{th} subject in the i^{th} sequence,
 $m = 1, 2, \dots, 6$

π_j = the j^{th} period effect, $j = 1, 2, 3, 4$

τ_k = the k^{th} treatment effect, $k = 1, 2, 3, 4$

e_{ijkm} = the random error associated with the m^{th} subject in sequence i who received treatment k in period j.

where $s_{im} \sim N(0, \sigma_B^2)$ i.i.d., $e_{ijkm} \sim N(0, \sigma_W^2)$ i.i.d. and s_{im} , e_{ijkm} are independent random variables.

Point estimates for the ratios of the geometric means (treatment A / treatment B) for the comparisons as stated in Section [7.1](#) and the primary endpoints (see Section [2.1](#)) with their two-sided 90% confidence intervals (CIs) will be provided.

For each endpoint, the difference between the expected means for $\log(A)$ - $\log(B)$ will be estimated by the difference in the corresponding adjusted means (Least Squares Means). Additionally, their two-sided 90% confidence intervals will be calculated based on the residual error from the ANOVA and quantiles from the t-distribution. These quantities will then be back-transformed to the original scale to provide the point estimate and 90% CIs for each endpoint.

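### Do the four planned comparisons leave out a contrast that the trial needs, namely whether the food effect differs between the two tablets?

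*SAP*

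**What the plan says.** Protocol 7.1 and SAP 7 (Main comparisons of interest) list the same four ratios of geometric means: i) T fasted/R fasted, ii) T fed/R fed, iii) T fed/T fasted, iv) R fed/R fasted. The SAP heads the list with "The main comparisons of interest in this trial to assess relative bioavailability are the following".

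The Protocol synopsis describes the comparisons as "for the two tablet formulations under fasted or fed condition and the food effect for each formulation". The objective in Protocol 2.1.1 is to compare the commercial tablet (iCF) with the trial tablet (TFII) "and to assess potential food effects following oral administration of BI 1358894".

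The mode of inference is set in Protocol 7.1: "Since the main focus is on estimation and not testing, a formal hypothesis test and associated acceptance range is not specified". The same section states that "no significance level adjustment for investigating multiple comparisons will be applied".

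Protocol 7.2.2 and SAP 7.4.1 fit one log-scale ANOVA to all four treatments: "This model will include effects accounting for the following sources of variation: sequence, subjects within sequences, period and treatment". Confidence intervals use its residual error and t quantiles. SAP 4 announces no change to the planned analyses.

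**The concern.** Every subject takes both tablets in both food states, so the trial is a complete two-by-two factorial within subjects. The four listed ratios hold only three independent pieces of information, because ii)/i) equals iii)/iv). That common quantity, the ratio of the two food effects, is the one not listed.

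A reader given a food effect for each tablet will naturally ask whether they differ, and comparing two separate intervals by eye is a poor way to answer. Protocol Table 7.5: 2 shows this for N=24 and gCV 25%. A food ratio of 115% has the interval (100.44; 131.67), which excludes 100%. A ratio of 100% has (87.34; 114.49), which includes it. One might conclude that only one tablet has a food effect. If that comparison were one of the trial's questions, the plan would leave it without a proper interval.

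**Working it through.** **1. Does any stated aim need the contrast?**

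| Stated aim | Comparison that answers it |
|---|---|
| iCF relative to TFII (Protocol 2.1.1), fasted or fed (synopsis) | i) and ii) |
| Potential food effects (Protocol 2.1.1), for each formulation (synopsis) | iii) and iv) |
| Difference in food effect between tablets | not stated in the readable text |

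The first two rows are fully covered. The third is not an aim that the documents set.

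**2. Reproduce the protocol's precision.** Inputs from Protocol 7.5: N = 24 or 20, gCV 25% (the figure given for Cmax), two-sided 90% CI, and a precision reached with 95% probability. With four periods, the residual degrees of freedom are 3N − 6.

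- σ = √ln(1 + 0.25²) = 0.2462
- SE of a pairwise log ratio = σ√(2/N)
- Half-width w = t(0.95; df) × SE × √(χ²(0.95; df)/df)

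For N = 24, df = 66: w = 1.668 × 0.2462 × √(2/24) × √(85.96/66) = 0.1353. The interval around 100% is (87.34; 114.49), exactly as printed.

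For N = 20, df = 54: w = 1.674 × 0.2462 × √(2/20) × √(72.15/54) = 0.1506, giving (86.02; 116.26). The lower limit agrees with the table. The printed upper limit of 110.44 does not fit the table's own lower limit, but this has no bearing on the present question. At gCV 15% and 20% the intervals around 100% agree with the tables to within 0.05 points.

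**3. Is the ratio of ratios available from the planned model?** On the log scale it is (T fed − T fasted) − (R fed − R fasted), a linear contrast of the four adjusted means. A design matrix for 24 subjects in a balanced four-sequence Latin square (order assumed, since the design figure is not shown) has 96 observations and 30 parameters, hence 66 df. In units of σ², it gives a variance of 2/24 for a pairwise contrast and 4/24 for the ratio of ratios. The contrast is therefore estimable on the same residual, with SE = σ√(4/N).

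**4. Can a reader recover it from the reported results?** The point estimate is exactly iii)/iv). With complete balanced data its log half-width is √(4/N)/√(2/N) = √2 times that of any reported pairwise interval. At gCV 25%, by the protocol's 95%-probability convention:

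| N | Pairwise w | w × √2 | Upper limit / estimate | 90% CI around 100% |
|---|---|---|---|---|
| 24 | 0.1353 | 0.1914 | 1.21 | (82.58; 121.09) |
| 20 | 0.1506 | 0.2130 | 1.24 | (80.81; 123.74) |

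At gCV 13%, the figure for AUC, the upper limit is 1.11 (N = 24) or 1.12 (N = 20) times the estimate. Without the 95%-probability factor, the figures at gCV 25% would be 1.18 and 1.20, which are not comparable with the protocol's tables.

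Applied to the pair of intervals from Table 7.5: 2 at N = 24, the ratio of ratios is 115/100 = 115%, with limits 115 × 0.8258 = 95.0 and 115 × 1.2109 = 139.3. The √2 rule thus corrects the misleading impression left by the two separate intervals.

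**5. Is this the question that only a four-way crossover can answer?** No. A fasted T-versus-R crossover estimates i) and a separate fed one estimates ii). Their ratio ii)/i) is the same quantity. With N subjects in each study and the same intra-subject variance, its log variance is 2σ²/N + 2σ²/N = 4σ²/N, equal to that in step 3. What such studies would not give within subjects is the food effect of each tablet, and the plan reports exactly that as iii) and iv).

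**The case for a change.** The best case for the contrast is that it costs almost nothing and guards against a misreading. It needs one estimate statement per endpoint, with no new data or model, and Protocol 7.1 already waives multiplicity adjustment. Naming it beforehand would avoid a post hoc choice. Judging by overlap can also hide a difference: at N=24 and gCV 25% two intervals separate only when the food effects differ by a factor above 1.1449² = 1.31, while the direct contrast excludes 1 from about 1.21. The √2 rule, moreover, is exact only for complete balanced data. Up to 4 drop-outs are allowed for, and the PK analysis set keeps a subject with a single parameter value from one period. With missing periods the rule is approximate, because the covariance of iii) and iv) is not reported.

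All of that is correct, and it makes the contrast a reasonable option. It does not show an error: no conclusion the trial sets out to draw rests on comparing iii) with iv). One supposed advantage also falls short. A subject-by-food effect common to both tablets cancels from the contrast, but the pooled ANOVA residual used for its interval would still contain that variance.

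**Conclusion.** The concern does not hold. The four ratios match the objective and the synopsis, and in an exploratory estimation trial without an acceptance range, following the plan as written gives sound answers to the questions it poses. The food-effect ratio is neither inestimable nor lost. It follows from the planned ANOVA, and for complete balanced data from the reported intervals, with a precision of 1.21 (N = 24) to 1.24 (N = 20) at gCV 25%.

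This rests on the protocol's gCV values, a common residual variance and a balanced four-sequence layout. It also cannot be said that the plan omits the contrast altogether. The SAP names only its main comparisons, and the public text skips from Protocol 7.2.3 to 7.2.5 and from SAP 7.5.2 to 7.7, so a further analysis there cannot be ruled out.
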